## **1.2.8 Laboratory and other investigations**

Not applicable.

## **1.2.9 Data management**

Data will be collected on REDCap software, and will be coded, monitored and verified.

## **1.2.10 Data analysis**

Perioperative characteristics will be examined among the groups using chi square test and fisher's exact test, where appropriate; mean and median VAS pain scores will be analyzed with Student's *t*-tests and non-parametric tests, respectively; mean and median overall satisfaction with pain control and provider reported ease of procedure via VAS scores will be compared using Student's *t*-tests and non-parametric tests, respectively; linear regression will be completed in multivariable analysis to identify predictors of pain. Complications and patient symptoms associated with lidocaine toxicitiy will be examined between the groups using chi square test and fisher's exact test, where appropriate.

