### 1.2.3 Subject recruitment and allocation

Subjects will be recruited from Stanford Gynecology Clinic in Palo Alto, California and at Planned Parenthood Mar Monte in San Jose, CA.

- At Stanford, potential participants will be identified by prospective chart review done by clinical research coordinators. Once identified, clinical research coordinators will obtain permission from provider to speak with participants.
- At Planned Parenthood, clinic staff will notify clinical research coordinators of potential participants.

To ensure even allocation across sites, two randomization schemes will be created, one for each site.

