#### **1.2.5 Admission procedure**

Eligible women will be screened and identified in two ways. The first will be via prospective chart review done by Stanford clinical research personnel. The second will be providers and clinic staff informing clinical research personnel of potential participants.

If potential participants meet inclusion criteria and permission has been granted by their provider, they will be approached by a clinical research coordinator who will review the study protocol and obtain informed consent. After obtaining informed consent, participants will be randomized to a study arm via computer-generated block randomization using REDCap

software. The provider and staff will be aware of arm allocation, but participants will remain blinded.

There will be two study arms:

Experimental:

- Syringe loaded with 12 mL of 1% lidocaine (120 mg); 22-gauge spinal needle
- 2 mL injected at the tenaculum site, either 6 or 12 o'clock superficially into the cervix
- The tenaculum is immediately placed at the previously injected site
- The remaining 10 mL are slowly injected into the cervicovaginal junction in two equal aliquots at 4 and 8 o'clock; the injection is continuous from superficial to deep (3 cm) to superficial (injecting with insertion and withdrawal)
- No wait time between injection and dilator insertion

Control:

- Syringe loaded with 20 mL of 1% lidocaine (120 mg); 22-gauge spinal needle
- 2 mL injected at the tenaculum site, either 6 or 12 o'clock superficially into the cervix
- The tenaculum is immediately placed at the previously injected site
- The remaining 18 mL are slowly injected into the cervicovaginal junction in two equal aliquots at 4 and 8 o'clock; the injection is continuous from superficial to deep (3 cm) to superficial (injecting with insertion and withdrawal)
- No wait time between injection and dilator insertion

Prior to the procedure, clinical research coordinators will obtain the following baseline information using REDCap:

- Demographics
  - Location of procedure
  - MRN
  - Date enrolled
  - First name
  - Last name
  - Date of birth
  - Age
  - Phone number
  - Race
  - Ethnicity
- Medical History (Physical Exam and Ob/Gyn History)
  - Height
  - Weight
  - BMI
  - First day of last menstrual period
  - Gestational age defined by U/S
  - Medication allergies
  - Current medications
  - Number of previous pregnancies
    - Number of previous vaginal deliveries

- Number of previous cesarean sections

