- Number of previous abortions
- Number of previous abortions after 16 weeks gestation
- Number of miscarriages
- Recent deliveries
- Medical problems
- Previous surgeries
  - Previous cervical surgeries
  - Other previous surgeries

The participant will then be prepped for the procedure. At that point, the clinical research coordinator will accompany participants throughout the duration of their procedure and obtain the following information:

- Procedure Data
  - Provider type (i.e. resident, fellow, attending)
  - Provider reported ease of procedure
  - Initial cervical dilation
  - Uterine position
  - Number of osmotic dilators placed
  - Total procedure time, as defined by speculum time
  - Digoxin given
  - Complications
    - Inability to dilate cervix
    - Seizure
    - Cardiac arrest
    - Structural trauma (uterine perforation, cervical laceration, etc.)
    - Hemorrhage (EBL estimation)
  - Administration of Mifepristone for cervical preparation
- Procedure VAS Data
  - Anticipated Pain: 30 minutes prior to procedure
  - Baseline Pain: Immediately prior to procedure
  - Block injection Pain: Immediately following injection, but prior to dilator insertion
  - Dilator Insertion Pain: Immediately following dilator insertion
  - Post-procedure Pain: 10-15 minutes following procedure
  - Overall Pain: Assessed after procedure (prior to discharge)
- Symptom Data
  - Following block injection, any experience of:
    - Metallic taste in mouth
    - Ringing in ears
    - Lightheadedness
  - Any other systemic symptoms experienced, including vasovagal reaction
- Acceptability Data
  - Global satisfaction with procedure
- Recognition of group allocation

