## **1.2.11 Number of subjects and statistical power**

88 participants are required to be 80% sure that the lower limit of a one-sided 97.5% confidence interval (or equivalently a 95% two-sided confidence interval) will be less than the non-inferiority limit of 15mm. Accounting for participant drop-out, we will recruit 96 women to participate in this study (significance level, alpha of 5%; power of 80%; standard deviation of 28; non-inferiority limit of 15).

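### The VAS comparison ignores the site stratification and two pre-block pain scores; a prespecified adjusted difference is a low-cost efficiency gain of unknown size

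*Combined protocol and SAP*

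**What the plan says.** Section 1.2.10 (Data analysis) states that "mean and median VAS pain scores will be analyzed with Student's" t-tests for means and non-parametric tests for medians. No covariate or stratification factor is named. The same section adds that "linear regression will be completed in multivariable analysis to identify predictors of pain"; it lists no covariates, does not say that arm is in the model, and does not link the model to the non-inferiority limit.

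Two design features bear on this:

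- **Site.** Section 1.2.3 says: "To ensure even allocation across sites, two randomization schemes will be created, one for each site". Section 1.2.5 specifies blocked randomization after consent.
- **Pre-block pain.** Section 1.2.5 lists "Anticipated Pain: 30 minutes prior to procedure" and "Baseline Pain: Immediately prior to procedure", both on the 0–100 mm VAS used for the primary outcome, pain at dilator insertion.

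On blinding, section 1.2.5 says: "The provider and staff will be aware of arm allocation, but participants will remain blinded". Section 1.2.11 sets the decision criterion: "88 participants are required to be 80% sure that the lower limit of a one-sided 97.5% confidence interval" will fall below 15 mm.

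**The concern.** The trial stratifies randomization by site and collects two pre-randomized-treatment measures on the outcome's own scale, but the stated between-arm comparison uses none of them. Under randomization the unadjusted difference is unbiased. If site predicts pain, ignoring the stratification usually makes the interval somewhat conservative, so validity is not in question.

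What is at stake is interval width. The conclusion depends on whether one confidence limit clears 15 mm, so a wider interval than necessary directly lowers the chance of showing non-inferiority when it is true.

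The open-ended regression does not fill the gap. An adjusted treatment effect whose covariates were chosen after the data were seen would carry little weight as evidence of non-inferiority.

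**Working it through.** **Inputs.** From section 1.2.11: SD 28 mm, limit 15 mm, 88 evaluable, one-sided 97.5% limit. Assumed, because the documents do not state them: 1:1 allocation (44 per arm), true difference 0, 28 mm as the total SD, and R², the share of outcome variance explained by the covariates.

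**The plan's own figure.** Number per arm = 2 × [28 × (z₁₋α + z₀.₈₀) / 15]².

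- One-sided 5%: 2 × [28 × (1.645 + 0.842) / 15]² = 43.1, so 44 per arm and 88 in total. This reproduces the plan; power at 88 is 80.7%.
- One-sided 2.5%, which is the 97.5% limit the text names: 2 × [28 × (1.960 + 0.842) / 15]² = 54.7, so 55 per arm and 110 in total. Power at 88 is 71.0%.

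The 71% starting point below therefore comes from a separate inconsistency in section 1.2.11.

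**Effect of adjustment.** Residual SD = 28 × √(1 − R²). Then:

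- SE = residual SD × √(2/44); with R² = 0 this is 28 × 0.2132 = 5.97 mm.
- Half-width of the 95% CI = 1.96 × SE.
- Power = Φ(15/SE − 1.96). With R² = 0: Φ(2.513 − 1.960) = Φ(0.553) = 71.0%. With R² = 0.25: SE = 5.17 mm and Φ(2.901 − 1.960) = Φ(0.941) = 82.7%.

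The t column uses the noncentral t distribution with 83 degrees of freedom (88 minus intercept, arm, site and two scores). The simulated columns fit the full model in 20,000 trials per row, assuming equal-sized sites, no site effect, and two independent scores sharing R².

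| R² | Residual SD (mm) | Half-width, normal (mm) | Power, normal | Power, t | Power, simulated | Mean half-width, simulated (mm) |
|---|---|---|---|---|---|---|
| 0 | 28.00 | 11.70 | 71.0% | 70.0% | 68.6% | 11.97 |
| 0.04 | 27.43 | 11.46 | 72.7% | 71.7% | 70.8% | 11.74 |
| 0.09 | 26.71 | 11.16 | 75.0% | 74.0% | 72.8% | 11.43 |
| 0.16 | 25.66 | 10.72 | 78.3% | 77.3% | 76.4% | 10.98 |
| 0.20 | 25.04 | 10.47 | 80.2% | 79.3% | 78.4% | 10.72 |
| 0.25 | 24.25 | 10.13 | 82.7% | 81.8% | 81.2% | 10.38 |

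In the same simulations the unadjusted t-test had power of 69.6% to 70.3% and a mean half-width of 11.8 mm. Simulation error is about √(0.7 × 0.3 / 20,000) = 0.3 percentage points.

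**Reading the simulated columns.** Against about 70% unadjusted, adjustment changes power by about −1 point at R² = 0, +1 at 0.04, +3 at 0.09, +6 at 0.16 and +11 at 0.25. The R² needed for 80% power is 0.196 by the normal formula, 0.214 on the t basis and about 0.23 by interpolating the simulation.

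**Adding a site effect.** If site explains an assumed 5% of the variance and the scores nothing, power is 71.4% adjusted against 70.5% unadjusted. If the scores also contribute R² = 0.09, it is 75.0% against 69.9%.

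**The other reading of alpha.** At one-sided 5% the normal-formula power with 88 rises from 80.7% at R² = 0 to 89.6% at R² = 0.25.

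**The case against.** A t-test is a legitimate prespecified analysis for a two-arm randomized trial, and nothing in the plan is contradicted by leaving covariates out. The benefit rests wholly on an R² that the documents do not supply. Baseline pain just before the procedure may cluster near zero and predict little; for R² of 0.04 or less the net change lies between about −1 and +1 point. The shortfall from 80% also depends on reading section 1.2.11 as a 97.5% limit. On a one-sided 5% reading, 88 already gives 80.7% and adjustment is a bonus. Finally, section 1.2.10 has a more basic gap: it specifies no between-arm difference, confidence interval or comparison with 15 mm, and a t-test does not by itself test against that limit.

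Most of this stands as qualification. It is a recommendation about efficiency; the gain may be small and should not be built into the sample size. It does not remove the case for the change, because the most that is lost is about 1 point and all the variables are already collected. The planned regression could include arm, site and pre-block pain, but the plan does not say so or give the model any role in the decision. The missing non-inferiority estimate strengthens the case, since the primary analysis has to be written out anyway.

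**Conclusion.** The concern holds as a recommendation to improve precision. The primary comparison leaves out the stratification factor and two pre-block scores that the trial already has. With 88 evaluable, SD 28 mm, no true difference, 1:1 allocation and a one-sided 97.5% limit, the adjusted model has power between 68.6% and 81.2% as R² goes from 0 to 0.25, against about 70% unadjusted. Where in that range the trial would fall cannot be determined from the documents. The gain is negligible at R² of 0.04 or below and material from about 0.16. Confidence that the change would make a practical difference is moderate.

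**What to change.** Write the following into section 1.2.10:

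- **Primary model.** Linear regression of dilator-insertion VAS on arm, site, baseline VAS and anticipated-pain VAS.
- **Estimate and decision.** The adjusted mean difference, 12 mL minus 20 mL, with its two-sided 95% CI; compare the upper limit with 15 mm. Higher VAS is worse, so for this contrast the upper limit is the relevant one, although section 1.2.11 speaks of the lower limit.
- **Sensitivity analysis.** The unadjusted difference and its CI.
- **Timing of the scores.** Record both before allocation is revealed or, failing that, before the block with the participant still blinded. Section 1.2.5 does not say how the scores are timed relative to randomization.
- **Missing pre-block scores.** Fill in the mean over both arms combined, so that no participant is lost. Section 1.5 expects scores to be hard to obtain on time.
- **Exclusions.** No variables measured after the block, such as number of dilators or procedure time.

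Reconcile alpha and sample size in section 1.2.11 separately; adjustment is not the remedy for that.

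The cost is a few sentences, some attention to clinic workflow if scores are to precede disclosure of the arm, three degrees of freedom, and about 1 point of power if the covariates explain nothing. No extra participants or measurements are needed.

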## **1.2.11 Number of subjects and statistical power**

88 participants are required to be 80% sure that the lower limit of a one-sided 97.5% confidence interval (or equivalently a 95% two-sided confidence interval) will be less than the non-inferiority limit of 15mm. Accounting for participant drop-out, we will recruit 96 women to participate in this study (significance level, alpha of 5%; power of 80%; standard deviation of 28; non-inferiority limit of 15).

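### The 88-participant sample size matches a one-sided 95% limit, not the stated one-sided 97.5% limit, so the claimed 80% power is about 71%

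*Combined protocol and SAP*

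**What the plan says.** The sample size is justified in one short paragraph, section 1.2.11. It gives the decision criterion as a "one-sided 97.5% confidence interval (or equivalently a 95% two-sided confidence interval"), and says that "88 participants are required to be 80% sure that the lower limit of a one-sided 97.5% confidence interval" "will be less than the non-inferiority limit of 15mm". The inputs follow in brackets: "significance level, alpha of 5%; power of 80%; standard deviation of 28; non-inferiority limit of 15". The bracket does not say whether the 5% is one-sided or two-sided. The paragraph then adds an allowance for losses: "Accounting for participant drop-out, we will recruit 96 women to participate in this study".

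Section 1.2.1 describes the trial as non-inferiority, and section 1.2.5 defines two arms. No allocation ratio and no assumed true difference are given. Section 1.2.10 (Data analysis) lists t-tests, non-parametric tests and regression, but names no confidence level and no non-inferiority criterion. Section 1.2.11 is therefore the only place where the decision interval is defined.

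**The concern.** The paragraph gives two significance levels that agree only if the 5% is two-sided. The sentence describes a one-sided error rate of 2.5%. The bracket says 5% without sidedness. In a non-inferiority calculation it matters which of these was entered, because only one side of the interval decides the result. If 5% was entered one-sided, the sample is too small for the interval that the text names.

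This is the only power statement for the primary comparison. If the trial reports the two-sided 95% interval, the risk of an inconclusive result is higher than stated. If it uses a 90% interval to keep 80% power, the one-sided type I error is 5%, twice what the named interval implies. Leaving both readings open would also let the interval be chosen after the data are seen.

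**Working it through.** **Inputs from section 1.2.11:** SD 28 mm, margin 15 mm, power 80%, total 88 before drop-out and 96 recruited. **Assumed, because not stated:** 1:1 allocation (44 or 48 per arm) and a true difference of 0.

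**Formula.** n per arm = 2 × [(z for 1 − α + z for power) × SD / margin]², with z = 0.842 for 80% power.

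**Reproducing the plan's figure (one-sided α = 0.05, z = 1.645).**
2 × [(1.645 + 0.842) × 28/15]² = 43.09, so 44 per arm and **88 in total**. This is an exact match. The t-based calculation also gives 88.

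**At the level the plan states (one-sided α = 0.025, z = 1.960).**
2 × [(1.960 + 0.842) × 28/15]² = 54.70, so 55 per arm and **110 in total**. The t-based calculation gives 112. The shortfall is 110 − 88 = 22 evaluable participants.

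**Power of the planned sample.** SE = 28 × √(2/n per arm), and power = Φ(15/SE − z).
- At 44 per arm, SE = 5.970 and 15/5.970 = 2.513.
- At 48 per arm, SE = 5.715 and 15/5.715 = 2.624.

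| Evaluable | One-sided 97.5% limit: normal (t) | One-sided 95% limit: normal (t) |
|---|---|---|
| 88 | Φ(0.553) = 71.0% (70.0%) | Φ(0.868) = 80.7% (80.2%) |
| 96 | 74.7% (73.8%) | 83.6% (83.2%) |

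**Other readings of 88.**
- A two-sided 5% two-sample formula gives 110.
- Equivalence by two one-sided tests gives 59.68 per arm, about 120 in total.
- Reading 88 as the number per arm gives 94% power at one-sided 2.5%.

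Of the variants tried, only one-sided 5% gives 88.

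**What would make 88 right at the stated level.** Either the SD would have to be 15 × √22 / 2.802 = 25.1 mm, or the margin 5.970 × 2.802 = 16.7 mm. The plan states 28 and 15, so this is not rounding.

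**Where the two readings diverge.** Take 44 per arm and an observed SD of 28. Non-inferiority is declared if the observed difference (12 mL minus 20 mL) is below 15 − 1.960 × 5.970 = 3.3 mm with the one-sided 97.5% limit, or below 15 − 1.645 × 5.970 = 5.2 mm with the one-sided 95% limit. A difference between 3.3 and 5.2 mm would pass under one reading and fail under the other.

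**The case against.** Several points can fairly be made for the plan.

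- **The 5% one-sided level is an inference.** The plan never says it was used. That is true, and the exact match at 44 per arm is the evidence for it. The discrepancy does not depend on the inference: 88 is too few for the stated level however it was obtained.
- **The contradiction is conditional.** With a true advantage of 16.7 − 15 = 1.7 mm for the 12 mL arm, 88 would give 80% power at one-sided 2.5%. This is possible in principle, but the plan claims no such advantage, and a zero difference reproduces its figure. Unequal allocation, or a true difference against the 12 mL arm, would lower power further.
- **71% is the lower end.** The primary score is taken immediately after dilator insertion and section 1.2.6 requires no follow-up, so losses may be few. Against this, section 1.2.7 discontinues some participants and section 1.5 expects difficulty in obtaining scores. A range of 71% to 75% is fair, and all of it is below 80%.
- **The bracket does say 5%.** A 90% interval would agree with the bracket read one-sided, so the doubled error rate is relative to the named interval, not to every statement in the paragraph. This stands as a point of wording. The two statements still conflict under that reading.
- **Inference stays valid if the named interval is used.** Type I error is then 2.5%, and only the risk of an inconclusive result rises. This is correct, and it is why a correction of the text is enough.

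**Conclusion.** The concern holds. Under the standard assumptions of 1:1 allocation and no true difference, the stated 88 participants, SD of 28, margin of 15 mm, 80% power and one-sided 97.5% limit cannot all be true. If alpha is one-sided 2.5%, the number is wrong (110 to 112 evaluable are needed). If alpha is one-sided 5%, the confidence level is wrong. No other section settles which was meant.

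With the named interval, power is about 71% at 88 evaluable (70% by t) and about 75% at 96 (74% by t). The risk of missing non-inferiority for truly equal blocks is thus 29% or 25%, against the 20% stated. A false power statement for the primary comparison must be corrected, although the correction is small.

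**What to change.** Keep the enrolment and the two-sided 95% interval, and rewrite the statement in section 1.2.11 with its assumptions, for example:

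> *Assuming SD 28 mm, margin 15 mm, 1:1 allocation and no true difference, 88 evaluable participants give about 71% power (about 75% if all 96 are evaluable) for the upper limit of the two-sided 95% confidence interval for mean pain, 12 mL minus 20 mL, to lie below 15 mm (one-sided alpha 2.5%).*

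This drops the unqualified 5% alpha. It also corrects the direction. On this scale higher scores mean more pain, so it is the upper limit of experimental minus control that must fall below the margin, whereas the present text refers to the lower limit. The power figures above are already for the upper limit.

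The cost is one corrected sentence and a less favourable stated power, with no extra patients.

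The sponsor could resolve the conflict in other ways:
- **Enlarge the trial.** At the plan's own allowance, 110 × 96/88 = 120 would be recruited (112 × 96/88 = 122.2, so 123, on the t-based figure). That is 24 more than planned, or about 24/11 = 2.2 months at the accrual rate in section 1.2.13.
- **Adopt a one-sided 95% limit openly.** This keeps 88 and 80% power, but it must be stated before the data are seen, with the 5% one-sided error acknowledged.

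A primary analysis adjusted for baseline covariates could recover part of the loss. To bring the residual SD from 28 to 25.1, the covariates would need R² = 1 − (25.1/28)² ≈ 0.20, a correlation of about 0.44 with the outcome. The documents give no such correlation, so this gain cannot be assumed.

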### **1.1.2 Objectives and hypothesis**

We hypothesize that a 2-site, 12 mL 1% plain lidocaine injection paracervical block (PCB) technique (2 mL for tenaculum placement, 10 mL for paracervical block) will provide non-inferior pain control compared to a previously established 2-site, 20 mL 1% lidocaine injection PCB (2 mL for tenaculum placement, 18 mL for paracervical block) when administered for dilation pain control during cervical preparation.

Our primary objective is to determine pain perceived at time of dilator insertion measured by Visual Analogue Scale (VAS; Dilator Insertion: Immediately following dilator insertion) (0-100mm).

Secondary objectives include assessing:

- Pain perceived at additional time points before, during, and after the procedure (all measured by VAS (0-100mm; 0 being no pain and 100 being worst pain imaginable):
  - o Anticipated Pain: 30 minutes prior to procedure

- Baseline Pain: Immediately prior to procedure
- Block injection Pain: Immediately following injection, but prior to dilator insertion
- Post-procedure Pain: 10-15 minutes following procedure
- Overall Pain: Assessed after procedure (prior to discharge)
- Total procedure time, as defined by speculum time
- Incidence of complications
  - Inability to dilate cervix
  - Seizure
  - Cardiac arrest
  - Structural trauma (uterine perforation, cervical laceration, etc.)
  - Hemorrhage (EBL estimation)
- Symptom Data
  - Following block injection, any experience of:
    - Metallic taste in mouth
    - Ringing in ears
    - Lightheadedness
- Any other systemic symptoms experienced, including vasovagal reaction
- Provider reported ease of insertion
- Global satisfaction (acceptability) of procedure reported by participant (VAS, 0-100mm; 0 being unsatisfied and 100 being fully satisfied)

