## 1.2 Design and methodology

### 1.2.1 Research design and General Methodological Approach

This is a non-inferiority, single blinded, randomized controlled trial.

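### The non-inferiority rule in 1.2.11 names the wrong confidence limit and 1.2.10 does not correct it; at the stated 95% interval, 88 evaluable participants give about 71% power, not 80%

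*Combined protocol and SAP*

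**What the plan says.** Section 1.2.1 fixes the design: "This is a non-inferiority, single blinded, randomized controlled trial". Section 1.1.2 gives the hypothesis, that the 12 mL block "will provide non-inferior pain control compared to a previously established 2-site, 20 mL 1% lidocaine injection PCB", and the primary outcome: "Our primary objective is to determine pain perceived at time of dilator insertion measured by Visual Analogue Scale", on a 0-100 mm scale. The anchors appear in the same section with the other pain time points: "0 being no pain and 100 being worst pain imaginable".

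The only statement of the success criterion is in section 1.2.11. It gives the size and the assurance, "88 participants are required to be 80% sure", and names the event to which this assurance applies: "lower limit of a one-sided 97.5% confidence interval (or equivalently a 95% two-sided confidence interval) will be less than the non-inferiority limit of 15mm". The inputs follow in brackets: "significance level, alpha of 5%; power of 80%; standard deviation of 28; non-inferiority limit of 15". Recruitment is set at 96 to allow for drop-out.

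Section 1.2.10 covers the primary outcome only within a general sentence: "mean and median VAS pain scores will be analyzed with Student's" t-tests and non-parametric tests respectively. It does not single out dilator-insertion pain, and it mentions no margin, confidence interval or non-inferiority rule. The opening pages, and whatever stands between 1.2.13 and 1.4, were not available for this review. No other section that was available states the rule.

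**The concern.** There are two separate faults.

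**Criterion.** On a scale where higher is worse, non-inferiority means ruling out an excess of pain of 15 mm or more with the smaller volume. That is a statement about the upper limit of the difference 12 mL minus 20 mL. A lower limit below 15 mm says only that the data do not prove the excess to be at least 15 mm. The analysis section does not repair this, because a t-test of no difference does not address non-inferiority and a non-significant result does not establish it. The trial's conclusion would then rest on a rule that does not test the hypothesis as worded.

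**Power.** Section 1.2.11 describes a one-sided 97.5% interval (alpha 2.5% one-sided) and also an alpha of 5% with no side given. The two lead to different sample sizes. If 88 was computed for the looser one, the trial has less than 80% power under the interval it describes. This does not make a false claim of non-inferiority more likely. It makes an inconclusive trial more likely.

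**Working it through.** **Inputs from section 1.2.11:** SD 28 mm; margin 15 mm; 88 evaluable; 96 recruited; power 80%; one-sided 97.5% (two-sided 95%) interval; alpha 5%, side not stated.

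**Assumed, not stated in the documents:** 1:1 allocation, hence 44 per arm (the most favourable split), and a true difference d (12 mL minus 20 mL) of 0.

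**1. Reproducing 88.** n per arm = 2 × (28/15)² × (z_alpha + 0.8416)², where 2 × (28/15)² = 6.969.

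| One-sided alpha | z_alpha | n per arm | Total |
|---|---|---|---|
| 5% | 1.645 | 43.09 → 44 | 88 |
| 2.5% | 1.960 | 54.70 → 55 | 110 |

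The plan's 88 reproduces exactly at one-sided 5%. It does not reproduce at the one-sided 2.5% that the stated interval implies.

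**2. Power at the planned size.** SE = 28 × √(2/n); power = Φ((15 − d)/SE − z_alpha).

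| Evaluable | SE (mm) | One-sided alpha | d | Power, normal | Power, noncentral t |
|---|---|---|---|---|---|
| 88 | 5.970 | 5% | 0 | 80.7% | 80.2% |
| 88 | 5.970 | 2.5% | 0 | 71.0% | 70.0% |
| 96 | 5.715 | 2.5% | 0 | 74.7% | 73.8% |
| 88 | 5.970 | 2.5% | −2 mm | 81.3% | – |
| 88 | 5.970 | 2.5% | +2 mm | 58.6% | – |

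For the second row: 15/5.970 − 1.960 = 0.553, and Φ(0.553) = 0.710.

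**3. What would rescue 80% at 88 evaluable and one-sided 2.5%.** Either of these:
- A true benefit of 12 mL: (1.960 + 0.842) × 5.970 − 15 = 1.72 mm (1.91 mm by t).
- A smaller SD: 15 / (√(2/44) × (1.960 + 0.842)) = 25.1 mm, against the stated 28.

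The documents assume neither. Without them, 80% needs 110 evaluable (80.2% by the normal formula, 79.5% by t), or 112 for 80.2% by t.

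**4. The decision rule.** The correct rule has two equivalent forms:
- 12 mL minus 20 mL: upper limit below +15 mm.
- 20 mL minus 12 mL: lower limit above −15 mm.

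A lower limit below +15 mm is neither. At 44 per arm and SD 28 the 95% half-width is 1.960 × 5.970 = 11.70 mm (11.87 by t). For 12 mL minus 20 mL:
- Correct rule: met when the observed excess is below 15 − 11.70 = 3.30 mm (3.13 by t).
- Rule as written: met when the observed excess is below 15 + 11.70 = 26.70 mm.

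With d = 0 the written rule would be met more than 99.9% of the time, so the stated 80% cannot refer to it. This indicates a slip in wording rather than an intended rule.

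**5. Why the t-test in 1.2.10 does not fill the gap.** At the same size and SD, an observed excess between about 3.1 and 11.9 mm (by t) would give a non-significant two-sided 5% t-test and yet fail the non-inferiority rule.

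**The case against.** The strongest reply is that no one would apply the rule literally. Design, direction of the hypothesis, scale, margin and interval level are all fixed in advance and fit only one sensible criterion. The confidence interval for a mean difference also comes from the same Student's t procedure that 1.2.10 names. This stands to the extent that the literal rule's behaviour should not be read as a realistic error rate. It does not remove the need for correction, because the sentence in 1.2.11 is the only statement of the rule and 1.2.10 neither restates it nor refers to it.

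On power, 88 is not an arithmetic mistake. It is right for one-sided 5%, and 1.2.11 does mention an alpha of 5%. The sponsor could keep 88 at 80% by adopting a one-sided 95% (two-sided 90%) interval. That route exists, but it loosens the error rate that the text spells out, in two equivalent forms, as 97.5% one-sided and 95% two-sided. The plan has to settle on one alpha, and the explicit interval is the safer reading.

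It is also fair to say that restating the power at 71% discloses the risk of an inconclusive trial without reducing it, and that this half matters less than the decision rule. Finally, the 3.3 mm threshold depends on the observed SD. By t at 44 per arm it is about 4.8 mm if the SD is 24 and 1.4 mm if it is 32.

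**Conclusion.** Both faults hold. The criterion in 1.2.11 is wrong as written under either sign convention, and no available section corrects it. It is probably a drafting slip, but it governs the trial's main conclusion and must be corrected before the data are analysed.

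At the interval the plan describes, 88 evaluable participants give about 71% power (70% by t-test), not 80%, and all 96 evaluable would give about 75% (74%). If the two volumes are truly equal, the chance of failing to show non-inferiority at 88 evaluable is about 29%, not 20%. These figures rest on SD 28, 1:1 allocation and zero true difference. A true difference of 2 mm in either direction moves power at 88 to between 59% and 81%, and unequal allocation would lower it.

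**What to change.** - **Decision rule, in both 1.2.10 and 1.2.11:** *Non-inferiority is concluded if the upper limit of the two-sided 95% CI for the mean difference in dilator-insertion VAS (12 mL minus 20 mL) is below +15 mm.*
- **Section 1.2.10:** identify this as the primary analysis and name the non-parametric comparison as supportive.
- **Section 1.2.11:** keep the 95% interval and 96 recruited. Give alpha as one-sided 2.5%, so that it agrees with the interval. Restate power as about 71% at 88 evaluable (about 75% if all 96 are evaluable), and state the assumed true difference of 0 and the 1:1 allocation.
- **For information:** 80% power at this interval would need about 110 evaluable (112 by t-test). At the drop-out implied by 88 of 96 (8/96 = 8.3%), that is about 120 to 123 recruited.

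The cost is wording in two sections and a less favourable stated power. The recruitment target, interval level and patient procedures do not change.
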